and slowly titrated up to maintenance dose. Gabapentin has been used successfully to treat neuropathic pain and perioperative pain ¹³. It has been shown to reduce stroke size, decrease the cortical spreading depression (CSD), which in turn can cause vasospasm and delayed ischemic neurologic deficit (DIND) ¹⁴. Mayo Clinic Jacksonville has been using gabapentin in order to reduce the narcotic requirement and complication. In our retrospective chart review in neurocritical care ICU (NICU) from January 2011 till February 2013, study (53 patients) there was 6% nausea (intolerable in 1.9%) but no major adverse effects of gabapentin maintenance dose (1800-2700mg /day). We also found a decrease in mean use of opioids with the use of gabapentin within the first 4 days post SAH compared to after 5 days (P = 0.01) . There was no fall, dizziness and abnormal liver function associated with the use of gabapentin. Aseptic meningitis was detected with the analysis of cerebrospinal fluid (CSF) during the second half of the ICU stay. The cost of 300mg of gabapentin was average of 30 times less than intravenous fentanyl 100 mcg. We did not find any other study looking at the use of gabapentin in aSAH patients.

The plan is to conduct a randomized control trial with a total of 20 aSAH patients. 10 aSAH patients admitted in NICU will be assigned to receive gabapentin, and 10 will receive placebo. Both of the groups will receive standard of care for pain control for 7 days.

Hypothesis: “Gabapentin will reduce the pain score and narcotics requirement_among hospitalized aSAH patients compared to placebo alone.”

The primary specific aims and hypothesis of this study are:

1. To compare the narcotic requirements among SAH patients experiencing headache treated with gabapentin or placebo for 7 days.
2. To compare efficacy of gabapentin in reducing the headache numeric pain score (NPS) compared to the non-GBP arm among hospitalized aSAH patients. Both groups are treated by an existing standard of care algorithm with narcotics and NSAIDs.

The secondary aims of this study are:

1. To evaluate the initial dose, escalation and side effects of gabapentin (nausea, vomiting, fall, lightheadedness, dizziness, vertigo, confusion).
2. To evaluate the incidence of delirium, vasospasm, delayed ischemic neurologic deficit (DIND) and seizure among hospitalized aSAH patients.
3. To evaluate the incidence of aseptic meningitis with cerebrospinal fluid (white blood cell and red blood cell ratio).

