intensity on day 5 of aSAH. GBP dosing was rapidly escalated within days of SAH up to a median of 1200 mg/day, with a range of 300 mg three times a day to 900 mg three times a day which was overall well-tolerated. Approximately 6% of patients treated with GBP had nausea (95% CI, 1-16%) that is also associated with SAH disease. Only 1 patient (1.8%) had to discontinue GBP due to nausea and vomiting. GBP dose was rapidly weaned similar to its tiered dose escalation or stopped after discharge in most of the patients. There were no major reported GBP withdrawal side effects such as seizure. However approximately, 4 patients had return of headaches observed after they weaned off the medication within a 30 day period in which case, GBP was resumed until headaches resolved. In 2 of these cases GBP was used for their outpatient management of baseline migraines or postoperative craniotomy headaches. In the Mayo Clinic study, visual analog scale (VAS) was used which is similar to NPS and was charted on a daily basis to document pain severity. VAS in these patients showed a slow rise from day one of aSAH until a maximum intensity around day 5. Two different peaks on day 11 and day 16 after aSAH were also noted subsequently. These peaks in VAS score also interestingly correlated with high CSF WBC/ RBC ratio and there were no culture proven bacterial or viral infection. This data suggests the inflammatory delayed headache pathophysiology of SAH headache and separate from the initial headache onset. These headaches also were more responsive to corticosteroids apparently since steroid use for breakthrough pain was noted during this time period. This data provides important insight that this period of time of post-SAH headache and meningismus may be a form of inflammatory or steroid- responsive aseptic meningitis.

Overall, the Mayo Clinic study demonstrated that GBP is safe and tolerable in aSAH patients with headache. No major adverse events (AE) were noted. A small portion of patients reported nausea that is inherent to SAH disease, and was managed conservatively with typical anti-nausea medications and did not require GBP discontinuation. The escalation of GBP in this population also appeared feasible and without major side effects. We saw decrease trends in use of opioid and steroids requirements with upward titrated and therapeutic doses of GBP.

C.2. Current Proposal Overview

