This study will be a randomized, placebo-controlled clinical trial enrolling 20 subjects at MCF to either GBP + standard of care (SOC) vs placebo + SOC arm. While enrolling the patients we will stratify patients via numerical pain score (NPS) to either <5 or ≥ 5 . Patients with an NPS ≥ 5 will be randomly assigned to either GBP or placebo group within 72 hours of SAH admission and after informed consent. The SOC pain regimen is comprised of intravenous (IV) fentanyl 25mcg to 50mcg q1hr PRN for head and neck pain as the first-line agent. If SAH pain remains >5 on NPS after the next nursing pain assessment, the next tier of pain agents will be utilized consisting of the following tier:

2nd line- enteral /PO oxycodone 5mg PRN q4hrs pain, and if still in pain after next assessment, then 10mg q4hrs PRN,

3rd line (if 2nd line failed to reduce NPS < 5)- IV 15mg ketorolac q6hrs PRN x 24hrs, unless serum creatinine > 1.3 , or GFR < 30 , or concern for gastrointestinal bleed risk, or history of bleeding peptic ulcer.

4th line (if 3rd line failed to reduce NPS < 5)- dexamethasone 2mg IV BID x 24hrs.

The patient will be enrolled within 72 hours of admission and meeting inclusion criteria by investigator and coinvestigators. Documentation of numeric pain score will be done by standard of care per nursing and hospital policies in the medical record. After consent and enrollment, a data collection sheet will be recorded by nursing to summate the NPS scores every 24 hours along with the SOC pain management plan. The SOC pain management plan will be implemented by the NeuroICU team of residents, attending, and nurse practitioners/PA's who are available on a 24/7 basis. A decrease in pain score equal or more than 50% will be defined as meeting the goal of the study, and as headache pain being under control. Patients will begin study medication (gabapentin or placebo) at approximately 9:00 AM on the morning following randomization into the trial to allow for documentation of the baseline average NPS. The

baseline NPS will be used to determine if the patient has had a 50% or more decrease in pain score.

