In patients with a normal creatinine clearance (CrCl) \geq 60 ml/min the study medication will be started at 100 mg three times a day and if headache is not controlled by study day #2, it will be increased to 300mg three times a day. For headaches that are still not controlled by day 3, study medication will be increased to 600 mg three times a day and by day 4, 900 mg three times a day. For the purposes of this study, a maximal dose of 900 mg tid in patients with normal kidney function (2700mg/day) even though the package insert describes 3600mg/day as maximal. For patients with a CrCl of 30 -59 ml/min, we will use an initial dose of 100mg tid day #1, then 200 mg tid by day #2 if pain uncontrolled, and 400mg tid if by day #3 if pain still uncontrolled. This dose of 1200mg/day would be the maximal dose used for these patients if CrCl remains within the 30-59ml/min range. We will exclude any patients who have CrCl $<$ 30 ml/min. When patients have achieved a 50% reduction of NPS, this will be defined as the maintenance dose and no escalation of GBP will be done after that, unless there is headache worsening. Placebo pills will be given three times a day and SOC pain management performed as indicated above in the control arm. The pharmacist or nurse will dispense the study drug. The bedside nurse will record the numeric pain score (NPS) 0-10, 0 being no pain and 10 being worst pain every 4 hours per hospital policy but done on a bedside data collection form as well for the purposes of the study. Total score over 24 hours will be averaged as daily score. Decision to increase the GBP will be based on 24 hour score communicated by the treating team as part of morning rounds by calling the central pharmacy.

After the 7 day study period, patients will be unblinded to either arm and those on gabapentin may remain on the medication if pain is controlled. However patients in the placebo arm-- if still in pain-- after 7 days may be treated with gabapentin up-titration similar to the treatment arm but used as standard of care. Patient's pain scores will also be recorded after the 7 day randomized period for observational purposes to examine for crossover effect (the proportion of those within the placebo arm who are placed on gabapentin). Analysis of these groups will be based on intention to treat principle.

C.3. Participants

Inclusion Criteria:

1. 18 years of age or older

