2. Have aneurysmal SAH diagnosed by CT scan of the brain and/or angiogram evidence of intracranial aneurysm (CTA or digital subtraction angiogram or MRA)
3. Have symptomatic headache
4. Able to swallow and verbalize pain score
5. No known allergy to GBP or fentanyl
6. Numeric pain score \geq 5
7. Ability to provide written personal consent

Exclusion Criteria:

1. GBP use prior to SAH admission
2. Renal failure with creatinine clearance less than 30 ml/min
3. Unable to receive standard of care pain medications
4. Pregnant patients
5. History of severe depression defined by DSM IV

C.4. Study Procedures & Schedule

All study medication will be labeled and dispensed according to subject number ensuring that treatment assignment remains concealed to the subject, investigator, and all study personnel who have subject contact. Data collection will be done in case report form at the bedside and

later will be enter in spread sheet. We will issue unique ID for each study patients. 20 preprinted study ID labels will be used to randomly select study patients.

Subject selection: All aneurysmal SAH admitted will be screened by the Mayo Cerebrovascular laboratory for eligibility and the NeuroICU attending and/or fellow will be contacted about potential enrollment in the study. Subjects who are able to provide written consent will be approached for enrollment. Based on prior volumes, we expect to have 20 subjects enrolled within 6-9 months.

Pain assessment: We will use numeric pain scale (NPS) that is been validated in many studies and is easy to use. Nurse and medical staff are familiar with this scale in our institute as it has been commonly used as standard of care. We plan to perform this pain scale every 4 hours in the study patients. The scale range from 0-10, 0 being the no pain and 10 being the worst pain ever. We will calculate daily total score for each patient. Only headache and neck pain will be included in the study to calculate the pain score. We will not include the score for other pain like back and abdominal pain.

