Gabapentin escalation dosing will be modeled after our retrospective safety study. We will start with 100 mg orally three times a day then every 24 hours increase to 300 mg tid as tolerated, then 600 mg tid and to a maximum of 900 mg tid. We plan to use 100mg tid then 200 mg tid and 400mg tid if creatinine clearance of 30 -59. We will exclude any patients who have CrCl <30. We will define maintenance dose of GBP as a dose in which after being on it for 24 hours there is 50% reduction of daily average NPS. We will continue maintenance dose throughout hospital stay. aSAH patients will be in observation in NICU for median of 15 days. The placebo will be escalated in the same manner as GBP. A Mayo pharmacist would dispense the study drug (ie., GBP or placebo). Every patients discharged with aSAH will be followed by Mayo neurologist as a SOC and they will plan to reduce or stop GBP.

C.6. Data Analysis

Unless otherwise specified, analyses will be performed using an intention-to-treat approach whereby subjects are analyzed according to randomized treatment arm. The primary endpoint for this trial will be the 7 days of treatment with or without GBP and best medical therapy. For this endpoint the treatment groups will be compared using a two-tailed test with a p -value ≤ 0.05 .

Categorical variables will be summarized as percentages, and continuous factors will be described using means or medians to best describe the distributions. Adverse events will be described as rates, and 95% confidence intervals estimated for those rates. The calculated total daily NPS score; opioid requirement and GBP dose will be analyzed. CSF WBC/RBC ratio will be calculated from the available sample and trended on days of SAH. All the plotted data will be projected with a 95% confidence interval.

We will compare the NPS, patient satisfaction score and the fentanyl requirement among the GBP and placebo group. We will use 2 sample t test or Wilcoxon rank sum test. The data will be analyzed to see if there is difference in incidence of aseptic meningitis, vasospasm and DIND between the GBP and placebo group. If there is difference more than 5 %, we will use regression modeling to analyze the data.

C.7. Sample Size Considerations

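### Entry is timed from admission and study day from first dose, neither from the bleed, and the comparison of pain and opioid use makes no use of SAH day

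*Combined protocol and SAP*

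**What the plan says.** **Entry.** C.2 sets the limit from admission twice: patients are "randomly assigned to either GBP or placebo group within 72 hours of SAH admission", and "The patient will be enrolled within 72 hours of admission and meeting inclusion criteria". The eligibility list in C.3 defines the disease by imaging ("Have aneurysmal SAH diagnosed by CT scan of the brain and/or angiogram evidence of intracranial aneurysm") and contains no limit on time since the bleed.

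**Study day.** Medication begins "at approximately 9:00 AM on the morning following randomization into the trial", and the interval before it is used to document the baseline NPS. Escalation is then counted in study days from the first dose, for example "if headache is not controlled by study day #2" (C.2).

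**Course of pain.** C.1.b reports the retrospective series by SAH day: a "slow rise from day one of aSAH until a maximum intensity around day 5", then further peaks on days 11 and 16. Section 2 also divides the opioid data by SAH day and gives P = 0.01 for what it describes as "decrease in mean use of opioids with the use of gabapentin within the first 4 days post SAH compared to after 5 days".

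**Analysis.** C.6 compares NPS, satisfaction and fentanyl between arms by a two-sample t test or Wilcoxon rank sum test, with no covariate. SAH day enters C.6 once, for the CSF WBC/RBC ratio, which is to be "trended on days of SAH". The conditional regression in C.6 follows the comparison of aseptic meningitis, vasospasm and DIND incidence and names no covariates. The only stratifier in C.2 is NPS below 5 versus 5 or more; since C.3 requires at least 5, it balances nothing among randomised patients.

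**The concern.** If pain follows a course set by the day since the bleed, the same study day means different things in different patients. A baseline taken early on the rise will tend to be followed by higher scores whatever the treatment; one taken later will not. That feeds into any change from baseline and into the 50% fall that C.2 calls the goal of the study and uses to fix the maintenance dose. With 10 patients per arm, start days can differ between arms by chance, and the spread adds noise in any case. The sponsor already regards SAH day as informative enough to organise the CSF data by it, but leaves it out of the comparisons that answer the two primary aims.

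**Working it through.** The plan gives no figure on timing to reproduce, so the check has three parts.

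**1. Windows.** Count the day of the bleed as SAH day 1 and assume admission that day. Earliest case: randomised on day 1, first dose on day 2, window days 2-8. Latest case: randomised at 72 h (day 4), first dose the next morning (day 5), window days 5-11; in hours, 72 + up to about 24 = about 96 h after admission. The two windows share days 5-8, which is 4 of 7. The day-5 maximum is study day 4 for the first patient and study day 1 for the second, whose study day 7 is the day-11 peak. Any delay between bleed and admission moves the window later. C.1.a calls the site a referral center, but no delay is stated.

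**2. Chance imbalance in start day, 10 versus 10.** Assume start days spread evenly over k consecutive days. SD of one start day = √((k² − 1)/12). SD of the difference between arm means = that SD × √(1/10 + 1/10). The probabilities come from the exact distribution of the difference.

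| Start days | k | SD of start day | SD of arm difference | P(gap ≥ 0.5 day) | P(gap ≥ 1 day) |
|---|---|---|---|---|---|
| 2-5 (no delay) | 4 | √(15/12) = 1.12 | 1.12 × 0.447 = 0.50 | 37% | 6% |
| 2-8 (delay 0-3 days, assumed) | 7 | √(48/12) = 2.00 | 2.00 × 0.447 = 0.89 | 62% | 29% |

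**3. Which outcomes feel it.** Peak heights are not given, so this is an illustration. Take the daily total NPS (six 4-hourly readings), a rise of A points from day 1 to day 5, later peaks at 0.8A on days 11 and 16, troughs at 0.4A on days 8 and 13.5, straight lines between, and no drug effect. Baseline is the SAH day before first dose. A = 6, 12 or 18 corresponds to 1, 2 or 3 NPS points × 6 readings.

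For A = 12, 7-day mean minus baseline is +7.37, +4.86, +2.14 and −0.77 for first doses on days 2, 3, 4 and 5. The 7-day means themselves are 7.37, 7.86, 8.14 and 8.23, which is almost flat.

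| A | SD from timing, change (starts 2-5) | SD from timing, 7-day mean (2-5) | SD, change (2-8) | SD, 7-day mean (2-8) |
|---|---|---|---|---|
| 6 | 1.52 | 0.17 | 1.92 | 0.24 |
| 12 | 3.04 | 0.33 | 3.84 | 0.49 |
| 18 | 4.55 | 0.50 | 5.76 | 0.73 |

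Add these to the plan's SD of 5.84 (C.7; unit not given, read here as daily total): total SD = √(5.84² + timing SD²). For change with A = 12 and starts 2-5, √(34.1 + 9.2) = 6.58. For an assumed 9-point difference (25% of an assumed daily total of 36), normal-approximation power at 10 per arm is 93.1% with SD 5.84. With timing spread over days 2-5 it is 91.5%, 86.4% or 77.6% for the three values of A; over days 2-8 it is 90.6%, 82.1% or 68.9%. For the 7-day mean, the worst case is √(34.1 + 0.53) = 5.89 against 5.84, under 1%.

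**What a covariate recovers.** Fit a straight line in start day to the A = 12 changes. For starts 2-5 the SD left over is 0.10, so 1 − (0.10/3.04)² = 99.9% of the timing variance is removed. For starts 2-8 (further changes −4.39, −2.54, −0.34) it is 2.16, so 1 − (2.16/3.84)² = 68%.

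**The case against.** **The test remains valid.** A reader might infer that the comparison is biased. It is not: start day is settled before treatment is assigned, randomisation makes it independent of arm on average, and chance imbalance is already within the test's 5% error. This stands, and it makes the point one of efficiency.

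**The effect on a 7-day mean is negligible.** C.6 does not say that NPS is analysed as change from baseline, and it names no between-arm test of the 50% fall. If the analysis is a plain 7-day mean, little is lost. This also stands. But C.6 does not settle on a 7-day mean either, and C.2 makes the 50% fall the goal of the study, so the affected measures are in play.

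**A late starter is not necessarily at the peak.** A reader might infer that a patient first dosed on SAH day 5 has a baseline at the maximum and falls regardless. C.2 takes the baseline before first dose, so it lies mostly on day 4, still on the rise; on the curve above the change is only −0.8. A clear fall (−4.4 for A = 12) needs a first dose on day 6, and hence a pre-admission delay that the documents do not report.

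**The pain and opioid data are not an untreated course.** All 53 patients in the series received gabapentin with other analgesics. The opioid sentence in section 2 can mean use by period or early versus late gabapentin, so it does not show that opioid use follows SAH day independently of treatment. This limits how far the curve can be trusted. It does not remove the reason to adjust for a baseline variable the sponsor itself uses to describe pain.

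**Conclusion.** The point holds as a loss of efficiency that is cheap to avoid. Entry and study day are both detached from the bleed, the treatment windows cover different parts of the sponsor's described pain course, and the NPS and fentanyl comparisons ignore this. With no pre-admission delay and evenly spread starts, a gap of half a day or more between arms is common (37%) and a gap of a day or more is not (about 6%); both rise with transfer delay. The consequence is mainly for change from baseline, the 50% goal and day-by-day scores. On an assumed curve and an assumed 9-point difference, the power loss with starts on days 2-5 runs from about 2 to 16 percentage points. It is overstated if 5.84 already contains timing variation, and nothing in the documents allows a figure for opioid use.

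A reader might also infer that the plan needs an entry limit counted from the bleed, or a randomisation stratum split at SAH day 4/5. The documents do not support requiring either: the first may exclude late transfers, and with same-day admission the second would put only the latest starters in the late group of a 20-patient trial.

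**What to change.** 1. Record the date and time of the bleed on the case report form. The CSF trend in C.6 already needs SAH day, so this is at most one added field.
2. In C.6, prespecify SAH day at first dose as a covariate in the arm comparison of NPS change, 50% response and opioid use. The t test and rank sum test have no place for a covariate, so name the model, for example a linear model for the continuous outcomes and a logistic model for response.
3. Plot NPS and opioid use by SAH day as well as by study day.

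**Cost.** A sentence or two in C.6 and one degree of freedom among 20 patients; nobody is excluded. A logistic model with 20 patients will be imprecise. A single linear term is enough on the assumed curve if starts stay within days 2-5, but may leave timing variation if starts extend past day 5, because the described course rises and falls. That should be acknowledged in the plan rather than met by choosing the form of the covariate after seeing the data.

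### Patients are randomised before the baseline average is documented and up to about a day before the first dose, with no re-check of eligibility, so an undosed patient can remain in the intention-to-treat comparison

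*Combined protocol and SAP*

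**What the plan says.** The order of events is in C.2 (Current Proposal Overview). Patients with an entry numeric pain score (NPS) of 5 or more "will be randomly assigned to either GBP or placebo group within 72 hours of SAH admission and after informed consent". Then: "Patients will begin study medication (gabapentin or placebo) at approximately 9:00 AM on the morning following randomization into the trial". The reason given for the wait is that an average pre-treatment score has to be recorded first. Of the use made of that average, C.2 says only that the baseline "NPS will be used to determine if the patient has had a 50% or more decrease in pain score". It is not used as a test of eligibility.

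The inclusion criteria in C.3 require an NPS of 5 or more and also "Able to swallow and verbalize pain score". No section repeats either check between randomisation and the first dose.

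C.6 sets the general rule, subject to stated exceptions: "analyses will be performed using an intention-to-treat approach whereby subjects are analyzed according to randomized treatment arm". The only later exclusion is in C.4, where patients who develop bacterial meningitis leave the headache analysis. C.4 provides 20 preprinted study labels and C.7 plans 10 patients per arm. Neither section makes any allowance for undosed patients or provides for their replacement.

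**The concern.** The plan qualifies the patient, randomises, completes the baseline, and only then gives the first dose. The first dose is fixed at about 9:00 AM the next morning, so the wait can approach 24 hours. A patient randomised between 10:00 and 17:00 waits 16 to 23 hours. These are patients in the first days after a subarachnoid haemorrhage, and their condition can change overnight.

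Two things can go wrong in the wait. First, a patient may become unable to swallow or to report a score. That patient has already been allocated, uses one of 20 labels, and under C.6 counts in the assigned arm. With 10 per arm, one such patient is 10% of an arm. Second, a patient who qualified on one score of 5 or more may have a lower baseline average, which leaves less room for the NPS to fall.

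The present order gains nothing in return. Baseline NPS does not depend on the arm, so it can be collected equally well before allocation.

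**Working it through.** **The plan's own figure.** C.7 states a 25% difference, an SD of 5.84, two-sided alpha 0.05 and 80% power, and concludes that fewer than 10 patients are needed. This cannot be reproduced uniquely because the mean to which the 25% applies is not given. An SD of 5.84 is too large for a 0–10 score (maximum about 5), so a daily total is the reading that fits. With six readings a day and assumed mean totals of 30, 36 or 42, the differences are 7.5, 9 and 10.5 points. These need 10, 7 and 5 patients per arm by the normal approximation. By the t test, power with 10 per arm is 78%, 90% and 97%. The point here does not depend on which reading is right, so I start from the plan's nominal 80%.

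**Undosed patients: how many.** The overnight loss rate p is an assumption. Only undosed patients in the gabapentin arm dilute the effect, so the relevant denominator is 10.
- Expected number = 10p: 0.5 at p = 5%, 1.0 at p = 10%.
- Chance of at least one = 1 − (1 − p)^10: 1 − 0.95^10 = 40%; 1 − 0.90^10 = 65%.

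**Undosed patients: effect on power.** With k of 10 gabapentin patients never treated, the mean difference is multiplied by (1 − k/10). One undosed patient leaves 0.9 of the effect, equivalent to losing 1 − 0.9² = 19% of the information. For a two-sample t test with 10 per arm, 80% power corresponds to a standardised difference of 1.325.

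| Undosed (k) | Power | Probability at p = 5% | Probability at p = 10% |
|---|---|---|---|
| 0 | 80.0% | 0.599 | 0.349 |
| 1 | 71.3% | 0.315 | 0.387 |
| 2 | 61.1% | 0.075 | 0.194 |
| 3 | 50.1% | 0.010 | 0.057 |

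The average power is the sum of power times probability, with k of 4 or more adding 0.04 and about 0.5 percentage points:
- p = 5%: 47.9 + 22.5 + 4.6 + 0.5 + 0.04 = about 75.5%.
- p = 10%: 27.9 + 27.6 + 11.9 + 2.9 + 0.5 = about 71%.

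This assumes that the patient receives no drug in the 7 days and that the outcome is still recorded. For a patient who can no longer give a score, the NPS comparison loses an observation instead. The dilution then applies to the narcotic comparison.

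**Baseline average below 5.** Scores are taken "every 4 hours per hospital policy", so the wait holds about 0 to 6 readings. I simulated rounded 0–10 scores with entry on one reading of 5 or more, a baseline equal to the mean of four later readings, between- and within-patient SDs of 1.5 to 2, and no trend. All of these inputs are assumptions.

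| Assumed population mean NPS | Share with baseline average below 5 |
|---|---|
| 8 | 2–5% |
| 7 | 6–10% |
| 6 | 15–18% |
| 5 | 25–33% |

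The result is sensitive to trend. At mean 6, an upward drift of 1 point over the wait gives 4–8%, and a downward drift of 1 point gives 33–38%.

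**The case against.** The order is not in dispute, but several stronger readings are tempting and the documents do not support them.

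- *That some patients will enter undosed or below 5.* This is a risk, not a documented fact, and no rate is given for either event. C.1.b reports severe headache in all patients of the retrospective series, with pain rising from day one to about day 5. That argues against a fall overnight. Standard-of-care analgesia during the wait pushes the other way, so the net direction is unknown.
- *That the chance of harm is 64 to 88%.* Those figures are 1 − 0.95^20 and 1 − 0.90^20, which count both arms. An undosed placebo patient forgoes no active drug and does not dilute the effect.
- *That the 50% criterion becomes undefined because baselines may reach 0.* In the untrended simulation an average of exactly 0 occurs in at most about 0.04% of patients, even at an assumed mean of 4. At mean 6, an average below 3 occurs in 1–2%. C.6 in any case compares NPS by t test or rank-sum test, not by percentage change.
- *That the arms are biased, or that undosed patients should be dropped.* The baseline precedes any study drug and allocation is concealed (C.4). Keeping undosed patients is correct under intention to treat.

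Three further limits stand. Nothing says that a patient who misses the 9:00 AM dose cannot start later, so a total absence of drug is the unfavourable case. The 80% starting point is nominal: with assumed mean totals of 30, 36 or 42, one undosed gabapentin patient leaves 69%, 83% or 93% power. C.2 also does not say when the baseline window opens, and scores are already charted as routine care, so the average may include readings from before randomisation.

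What remains is the avoidable gap between allocation and first dose, with no rule for what happens in it.

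**Conclusion.** The point holds as a weakness of sequence that is cheap to remove. Randomisation comes before the baseline is documented and up to about 24 hours before the first dose. Eligibility is not re-checked, and everyone randomised is analysed. The consequence is possible dilution and lost precision, with no bias between arms.

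At an assumed overnight loss of 5–10%, there is a 40–65% chance of at least one undosed gabapentin patient, and average power falls from 80% to about 75.5–71%. The 61% for two undosed patients is a less likely case (probability 7.5–19%). All of this rests on the assumed loss rate, on no drug being given at all, and on a nominal 80% start.

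The share of patients with a baseline average below 5 runs from about 2% to 33% over assumed mean scores of 8 down to 5, before any trend, and the documents cannot narrow it. A reader might infer that the entry threshold must therefore apply to the average. That does not follow: it would change the population studied and could exclude many consenting patients if mean pain is moderate.

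**What to change.** In C.2, change the order to:
1. consent;
2. baseline NPS collection;
3. just before the first dose, confirmation that the patient still meets the existing criteria of being able to swallow and to verbalise a score;
4. randomisation;
5. first dose at about 9:00 AM, as now.

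State that consented patients who fail step 3 are not randomised and use no study label. State also which event the 72-hour limit governs, because C.2 attaches it both to random assignment and to enrolment, and under the new order these can fall on different days.

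The cost is protocol wording, same-morning release of the allocation by the pharmacy, a brief confirmation at the bedside, and slightly slower enrolment because a few consented patients will not be randomised. The readings are those already planned, and the sample size stays at 20. Applying the threshold of 5 to the baseline average is for the sponsor to decide separately and is not part of this change.
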